**Protocol Title: Trial to Improve Multisensory Neural Processing, Language & Motor Outcomes in Preterm Infants**

**Study Summary**

|   |  |
|---|--|
| Project Title                              | Trial to Improve Multisensory Neural Processing, Language & Motor Outcomes in Preterm Infants   |
| Project Design                             | Randomized Controlled Trial  |
| Primary Objective                          | To demonstrate that preterm infants receiving a standardized, parent-supported, auditory-tactile intervention in addition to standard of care in the NICU will have more typical cortical multisensory processing at discharge to home and better sensory adaptation and motor and language outcomes than infants receiving only standard of care. |
| Secondary Objectives                       | To test the role of multisensory responses at discharge in mediating intervention effects on later sensory adaptation, and motor and language outcomes. To explore the role of m responses in mediating intervention effects on later motor and language outcomes.   |
| Research Interventions/Interactions        | Listed in Table 1 on page 4  |
| Study Population                           | Preterm infants 32-36 weeks postmenstrual age(PMA)   |
| Sample Size                                | 230  |
| Study Duration for individual participants | NICU intervention between 32-36 week PMA/Follow up at 3 months to 2 years of age   |
| Study Specific Abbreviations/ Definitions  | Bayley III – Bayley Scales of Infant Development 3 rd edition
BCQ – Baby Care Questionnaire
HNNE – Hammersmith Neonatal Neurological Examination ITSP – Infant Toddler Sensory Profile
MSP – Multisensory Procedures
PLS5 – Preschool Language Scales 5 th edition   |

**Protocol Title: Trial to Improve Multisensory Neural Processing, Language & Motor Outcomes in Preterm Infants**

|                       |  |
|-----------------------|--|
|                       | PSDQ – Parenting Styles and Dimensions Questionnaire
STS – Skin to Skin |
| Funding Source | National Institute of Child Health and Development                         |

**Table 1**

| Construct   | Procedure(s)                     | Timing                              | Variable derived   | Variable type |
|--|---|--|---|----------------------|
| Multisensory response (Auditory-Tactile processing) | ERP to simultaneous puff + speech sound | Pre and post intervention (near discharge) | Pre-Post change in amplitude at frontal scalp locations in 176-377 ms time window                           | continuous           |
|  |   |  | IMP: Percentage of time spent in near-typical neural activation   | continuous           |
| Sensory reactivity and adaptation to environment    | ITSP                                    | 9-12 months                                | Behavioral neurological threshold score (typical or atypical)   | nominal              |
|  |   |  | Raw score in sensory processing domain  | continuous           |
| Language  | Bayley III                              | 22-26 months                               | Composite standard score
Scaled standard scores for expressive and receptive components                  | continuous           |
| Motor   | Bayley III                              | 22-26 months                               | Composite standard score
Scaled standard scores for fine and gross components                            | continuous           |
|  | Neurological Exam                       | 9-12 months
22-26 months                |   |                      |
| Tactile processing                                  | ERP to calibrated air puff              | Baseline/
After intervention            | Amplitude of response in 171-240 time window at central and frontal scalp locations                         | continuous           |
| Functional tactile connectivity                     | ERP to calibrated air puff              | Baseline/
After intervention            | Absolute clustering coefficient of alpha band coherence network   | continuous           |
| Speech Sound differentiation                        | ERP to 6 speech sounds                  | Baseline/
After intervention            | Difference in absolute amplitude between /du/ and /gu/ in frontal scalp locations in 250-350 ms time window | continuous           |

## **Introduction**

### **Background and rationale**

Every year, half a million infants are born prematurely in the United States and 15 million worldwide. The vast majority of preterm infants will have only moderate to mild impairments or delays in early childhood, with intellectual and behavioral consequences of prematurity only apparent at school age and beyond. These infants contribute most of the societal and economic burden of preterm birth, yet have often been overlooked in the face of other devastating and immediately visible consequences of extreme prematurity. Almost all preterm infants suffer from atypical brain maturation and its developmental consequences resulting from interactions between brain immaturity and premature extra-uterine sensory experience.

Brain development in the neonatal period is experience-dependent, yet the neonatal intensive care experience is largely comprised of atypical sensory stimuli. The critical importance of establishing functional sensory systems in infancy as the basis for all higher order processes (cognition, communication, behavioral adaptation) has been demonstrated in both animal models and humans. Preterm infants at discharge to home often have altered sensory reactivity and modulation in response to their environment, which are associated with negative neurodevelopmental outcomes in childhood. For the auditory system, preterm infants with deficient exposure to infant-directed speech sounds have poorer brain microstructure at discharge and worse neurodevelopmental outcomes at two years. For the tactile system, preterm infants with higher numbers of painful experiences have worse processing of light touch at discharge, decreased thalamic organization, decreased behavioral reactivity to tactile stimuli in the home environment, and less typical multisensory processing. Finally, brain responses to multisensory stimuli are supra-additive (greater than the sum of brain responses to unisensory stimuli).

Parents are critical in scaffolding early learning and development, especially with regards to early sensory exposures and responses. In particular, parental linguistic input is a key concept in learning language. Importantly, this input is more effective when it is contingent and immediate (i.e., language is presented immediately after infant action). This precept holds true even in early pre-linguistic phases, when infants differentiating among speech sounds, which is necessary for later development of higher-order language milestones.

## **Protocol Title: Trial to Improve Multisensory Neural Processing, Language & Motor Outcomes in Preterm Infants**

---

Another type of scaffolding provided by parents is the multisensory support of skin-to-skin (STS), which helps maintain quiet and alert states in immature infants who have frequent autonomic instability. Unfortunately, providing STS is often challenging for parents who often have to travel long distances to see their infant, while balancing responsibilities of other children and jobs, in addition to potential unreliable transportation and/or lack of social support.

Multisensory processes (MSPs) are rarely studied in neonates, yet in children and adults MSPs are essential to building a coherent and unified perception of the world, a foundation for learning and social interactions. In order to improve multisensory systems function of hospitalized preterm infants, further research is needed to design rigorous, standardized and mechanistically-based multisensory interventions using feasibly modifiable sensory exposures. There are currently no interventions that address rehabilitation of sensory function in the neonatal period, when brain-plasticity is at its greatest and when improvements can have an exponential downstream effect on later neurodevelopment.

The few associative studies, while critical, have not examined causal effects of interventions on neural processing changes to mediate neurodevelopmental outcomes. Fortunately, more infant-directed speech is associated with better language outcomes in the first 18 months and increased STS care with improved autonomic system stability and muscle tone in the hospital, and improved behavioral and motor outcomes in infancy. However, ours is the first study to use brain-based measures to test predictions regarding how the brain changes in response to multisensory treatment, which in turn affects functional outcomes.

Our study is in direct response to the NIH announcement calling for applications that “elucidate the mechanisms and/or behavioral outcomes of multisensory processing, the integration or processing of at least two distinct types of sensory input” (PA-15-347). In addition, our study meets two of the top new research priorities of the National Center for Medical Rehabilitation Research, to “Explore multimodal approaches that promote plasticity and sensorimotor function” and to “Develop objective measures to monitor functional progress.”

To accomplish these goals, our team has leveraged expertise in high-density functional EEG in the NICU, showing that we can rapidly and non-invasively acquire large datasets of brain-based sensory measures and analyze them with innovative spatiotemporal computational tools.

We have utilized these methodologies in pilot studies demonstrating that speech sound differentiation of preterm infants improves in response to a parent-supported standardized

## **Protocol Title: Trial to Improve Multisensory Neural Processing, Language & Motor Outcomes in Preterm Infants**

---

language intervention and that preterm infants exposed to STS care have increased multisensory processing efficiency compared to those who do not.

We have now designed a prospective, interventional RCT in preterm infants aimed at restoring more typical multisensory, rather than the unisensory, processing measures that were the outcomes of our pilot studies.

Our multisensory intervention using parents' voice and nurturing touch can be administered regularly in the NICU during sensitive periods of sensory development, even when parents cannot always be present. Our test of this multisensory intervention will involve 23 sessions of standardized, therapist-administered, auditory-tactile stimulation. This treatment will combine contingent presentation of recorded mother's voice delivered using a suck-activated system during holding with supportive tactile containment against the therapist's chest. This treatment will be tested in an internally-valid RCT. In addition to testing the efficacy of the treatment on gold-standard measures of language and motor functioning, we will also test whether the treatment effect is due to intermediate treatment effects on multisensory and unisensory processing. Understanding the mechanism by which the treatment works is important for laying the foundations of future improvements and potential recommendations for treatment that might be useful for wide-spread use even in lower resource settings with the ultimate goal of improving neurodevelopmental outcomes for these premature infants.

### **Methods and Analysis**

#### **Study aims**

Our aims for this study are first, to demonstrate that preterm infants receiving a standardized, parent-supported, auditory-tactile intervention in addition to standard of care in the NICU will have more typical cortical multisensory processing at discharge to home and better sensory adaptation and motor and language outcomes than infants receiving only standard of care. Second, to test the role of multisensory responses at discharge in mediating intervention effects on later sensory adaptation, and motor and language outcomes. Finally, to explore the role of m responses in mediating intervention effects on later motor and language outcomes.

#### **Study design and setting**

In order to test these aims, we are conducting an RCT of a multisensory (MS) intervention with 230 hospitalized preterm infants. Infants starting at 31 weeks will be randomized to either the control or intervention group. Both the control and intervention groups will receive standard care. Infants assigned to the MS group will also receive the MS intervention over two weeks,

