### **Study procedures**

For infants who meet inclusion criteria at 31 weeks, consent is obtained and parent's voice is recorded and parent-scented T-shirt may be collected when possible. Study staff may approach parents of eligible infants about the study and obtain consent slightly before the infant is 31 weeks, however, other study procedures will not start until the infant reaches 31 weeks. Infants are then randomized to the control or intervention group. If a patient is randomized to the control group, parents will be given the opportunity to consent to the secondary part of the study if they are interested. This part of the study is observational only and does not influence randomization. ERP testing is performed prior to the intervention. Infants assigned to the MS group receive the standardized MS intervention over 2 weeks, starting at 32 0/7 weeks PMA or at enrollment prior to 36 weeks. For both control and intervention groups, standard care includes skin-to-skin care on parent, when present, and playing of parents' voice non-contingent on infant suck. Parents may be asked to complete the Baby Care Questionnaire (BCQ) during infant's stay in the NICU or as soon as possible after discharge. Prior to the infant's discharge, a brief neurological examination (HNNE) and motor assessment (GMA) may be completed. ERP is repeated after intervention is completed, which occurs at 36 weeks PMA on average.

All infants are seen at the NICU Follow-Up Program clinics at 3-4, 9-12 (Year 1) and 22-26 months (Year 2). At the 3-4 month visit, study staff may obtain the Baby Care Questionnaire (BCQ), a brief neurological exam (HINE), and a brief motor assessment (GMA). At the Year 1 visit, study staff may obtain the BCQ, Infant Toddler Sensory Profile (ITSP), HINE, GMA, Bayley III, and the Parenting Styles and Dimensions Questionnaire (PSDQ). At Year 2, study staff may obtain the the Bayley III, HINE, BCQ, CBCL, PSDQ, and PLS-5.

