### **Inclusion and Exclusion Criteria**

The study population was originally comprised of 200 preterm infants. Due to Covid 19 losses to follow up, this number has been revised to 230 preterm infants. We anticipate the distribution to be 45% male and 55% female, as females have a small survival advantage after extreme prematurity. All races and ethnicities will be included, with an expected skew towards slightly more black children due to disproportionate effects of prematurity on race.

Inclusion criteria includes PMA 32 0/7 weeks gestation-36 0/7 weeks gestation. Exclusion criteria will be ventilation using an endotracheal tube, major congenital malformations, family history of genetic hearing loss, and use of sedatives or seizure medications. These medications may mask sensory processing as assessed by ERPs.

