## **Protocol Title: Trial to Improve Multisensory Neural Processing, Language & Motor Outcomes in Preterm Infants**

---

*In addition to randomization, we have addressed the problems of RCT design as follows:*

*Adherence to treatment protocol:* A highly manualized treatment for the MS treatment while monitored control treatments will be used by hospital staff during NICU hospitalization. These measures should help ensure uniform, high-quality implementation of the MS treatment. Sufficiently and randomly sampled fidelity of treatment (FOT) measures will be collected. Two of the first twelve MS sessions will be video recorded for study team review to ensure FOT. Treatment is provided in the NICU by experienced staff therapists.

*Total attrition:* Total attrition is expected to be less than 10% We have experienced <5% data loss due to non-compliance with electrode placement in our prior studies. Should motion artifact occur, we will retest patients with insufficient data within 24 hours. For the Bayley, should children prove unable to complete follow-up testing during scheduled visits, they will be rescheduled within one week of the scheduled visit. Testers are trained to perform the Bayley III in the home environment, if necessary, The ITSP can be performed over the phone or through the mail if necessary and will be performed within one week of a missed visit.

The BCQ and PSDQ may be completed by the parent in writing or via phone. Analysis will follow an intent-to-treat protocol. As such, all randomized participants will be analyzed and missing data will be handled using multiple imputation.

*Differential attrition:* Differential attrition is unlikely because children must be in the NICU during the treatment phase due to health concerns. There are no non-NICU treatments during the treatment phase. Thus, compensatory responses due to parental displeasure of group assignment is unlikely.

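### Randomisation opens at 31 weeks, before the stated 32 0/7-36 0/7 inclusion window and, by the listed order of steps, before the baseline ERP, with no eligibility re-check

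*Combined protocol and SAP*

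**What the plan says.** Four parts of the combined protocol and SAP bear on this.

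- **Time of randomisation.** Study design and setting: "Infants starting at 31 weeks will be randomized to either the control or intervention group". Study procedures has eligibility judged at the same age: "For infants who meet inclusion criteria at 31 weeks, consent is obtained and parent's voice is recorded". It adds that, apart from approach and consent, "other study procedures will not start until the infant reaches 31 weeks. Infants are then randomized to the control or intervention group".
- **Eligibility.** Inclusion and Exclusion Criteria: "Inclusion criteria includes PMA 32 0/7 weeks gestation-36 0/7 weeks gestation". The Study Summary also gives the study population as 32-36 weeks PMA. The exclusions are: "Exclusion criteria will be ventilation using an endotracheal tube, major congenital malformations, family history of genetic hearing loss, and use of sedatives or seizure medications". The section warns that these medications may mask the ERP response. It gives no date at which the exclusions apply.
- **Baseline ERP and treatment start.** After the randomisation step, Study procedures says "ERP testing is performed prior to the intervention". The intervention then runs over two weeks, "starting at 32 0/7 weeks PMA or at enrollment prior to 36 weeks".
- **Analysis.** The total-attrition paragraph under Randomization sets an intent-to-treat analysis in which "all randomized participants will be analyzed and missing data will be handled using multiple imputation". Table 1 defines one primary variable as a pre-post change in amplitude. Power/Sample Size makes the pretreatment ERP a covariate in every case.

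**The concern.** An infant at 31 weeks cannot satisfy an age criterion that begins at 32 0/7. As written, either the criterion is misstated or every infant randomised before 32 0/7 departs from it.

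The order of steps also opens an interval between allocation and the first point at which the infant can be tested and treated. Two exclusions can arise in that interval: endotracheal ventilation, and use of sedatives or seizure medications. An infant who meets one of them after allocation is still analysed, perhaps untreated or with a masked ERP. An infant with no usable baseline needs an imputed value for a quantity that enters both the change score and the adjustment, and the plan gives no imputation model. Much of this is avoidable, because the baseline ERP is already scheduled before treatment and could precede allocation.

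**Working it through.** **Step 1: set the ages side by side** (31 weeks is read as PMA, as the context implies).

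| Event | Stated timing | Section |
|---|---|---|
| Eligibility judged, consent, voice recording | 31 weeks (approach and consent may be slightly earlier) | Study procedures |
| Randomisation | from 31 weeks | Study design and setting; Study procedures |
| Baseline ERP | before the intervention; listed after randomisation | Study procedures |
| Intervention start | 32 0/7, or at enrolment before 36 weeks | Study procedures |
| Inclusion age | 32 0/7 to 36 0/7 | Inclusion and Exclusion Criteria |

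An infant randomised at 31 0/7 is 7 days short of the inclusion age. An infant enrolled at or after 32 0/7 raises no age conflict. No section describes a second eligibility check, requires a usable baseline ERP before allocation, or says how infants who become ineligible are handled.

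**Step 2: reproduce the plan's power.** Inputs from Power/Sample Size and Statistical Analysis: 230 infants, 1:1, 10% attrition, 1-tailed test, g = 0.74 (pilot) and g = 0.35 (minimum). Alpha is not stated; 0.05 is assumed. With n per arm and SD = 1:

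power = Φ(g × √(n/2) − 1.645)

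- N = 180 (n = 90), g = 0.74: Φ(0.74 × 6.708 − 1.645) = Φ(3.319) = 99.95%. The plan's figure of over 99% reproduces.
- N = 180, g = 0.35: Φ(2.348 − 1.645) = Φ(0.703) = 75.9%. The plan's figure of over 80% does not reproduce without a gain from baseline adjustment (a correlation of about 0.33 would be needed, and none is stated).
- N = 207 (n = 103.5), g = 0.35: Φ(0.35 × 7.194 − 1.645) = Φ(0.873) = 80.9%.

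The plan's 180 is 0.9 × 200; with the current 230, 0.9 × 230 = 207. That is a separate matter. N = 207 is used below because it follows from the current sample size and favours the plan.

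**Step 3: illustrate dilution.** Let q be the share of the intervention arm that stays in the analysis with an outcome but no treatment effect. The effect becomes g(1 − q). The documents give no value for q, so the range is assumed.

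| q (assumed) | g(1 − q) | Power, N = 207 | Power, N = 180 | Sample size factor 1/(1 − q)² |
|---|---|---|---|---|
| 0 | 0.350 | 80.9% | 75.9% | 1.00 |
| 2% | 0.343 | 79.5% | 74.4% | 1.04 |
| 5% | 0.3325 | 77.3% | 72.1% | 1.11 |
| 10% | 0.315 | 73.3% | 68.0% | 1.23 |

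At the pilot effect of 0.74, power stays above 99% for every q in the table.

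The formula covers untreated infants with outcomes. It does not cover missing baselines, which cost precision and add reliance on imputation but do not shrink g in proportion.

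**The case against.** The case against is substantial, and most of it limits the point.

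- **31 weeks is a floor.** Later enrolment is allowed, so only part of the sample is exposed. The Study Summary also uses 32-36 weeks for the intervention period, so the inclusion line may be a loosely worded treatment window. This stands as a limit on scope; the sections still conflict.
- **The ERP order is inferred.** The text ties the baseline ERP to the intervention only. Nothing requires it to follow randomisation, but nothing requires it to come first. This stands.
- **Intent-to-treat is right.** Keeping everyone randomised is correct. Intubation or sedation can also occur after 32 weeks, so later randomisation shortens the exposure without removing it. This stands.
- **A lost baseline need not lose the infant.** Aim 1 tests processing after the intervention, with the baseline as a covariate. This stands in part: Table 1 still defines an amplitude change.
- **Attrition is already allowed for.** N = 207 has had 10% removed, and infants who withdraw belong there. So q must count only those who remain in the analysis.

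A reader might infer that baselines are biased or lost differently by arm, because control parents are offered the secondary study straight after allocation. The documents do not show this. Under Randomization, examiners are blind except for parent reports, and concealment from staff who could influence scores is intended. Infants with insufficient ERP data are retested within 24 hours. No arm-specific treatment precedes the baseline. A reader might also quote two-sided power (about 71% at N = 207 with no dilution), but that drop comes from changing the plan's 1-tailed test and has nothing to do with the gap.

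**Conclusion.** The point holds in a limited form. The sections contradict each other on age at randomisation, and this needs no assumption. The listed sequence permits allocation before the baseline ERP and before time-varying exclusions can be re-checked at treatment start. The harm is avoidable dilution and avoidable imputed baselines. Differential loss and measurement bias are not demonstrated.

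The size is unknown because the affected share is not given. If 2% to 10% of the intervention arm were diluted in this way, power at g = 0.35 would fall by about 1 to 8 percentage points from 80.9%. This rests on a one-sided alpha of 0.05, N = 207, no gain from baseline adjustment and the assumed q. If the pilot effect is true, the loss of power is negligible.

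**What to change.** 1. **Reconcile the text.** Make Study design and setting, Study procedures, and Inclusion and Exclusion Criteria agree on the age at which an infant is eligible and may be randomised, and give the date at which each exclusion applies.
2. **Remaining infants.** Keep consent and voice recording at 31 weeks. Randomise only after the stated inclusion criteria are met, the exclusions have been re-checked and the scheduled baseline ERP is recorded.
3. **Infants already randomised.** Keep intent-to-treat as the primary analysis. Prespecify a sensitivity analysis for infants who became ineligible before treatment start or lack a baseline ERP. Identify them blind to arm, using a reference date that is defined in the same way for controls. Report their number by arm, which would replace the assumed q.

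**Cost.** A protocol amendment, with no added tests or staff. Scheduling becomes tighter between baseline ERP, allocation and first session. Infants before and after the amendment will have been randomised under different timing, so the date of change must be documented.
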